The FallMAP sessions will be delivered in room 201 of the Curtin Health and Wellness Centre, [name]. The Health and Wellness Centre has easy access in terms of public transport, (limited) patient parking and physical access.

The main research activities will be performed at the School of Physiotherapy and Exercise Science, Faculty of Health Sciences, [name] (CI).

Quantitative data collection

Participants who are willing and eligible to participate will be invited to undergo a one-hour baseline assessment in the week prior to commencement of the FallMAP programme. During this assessment eligibility will need to be confirmed. The first test during this baseline assessment will be the Standardised Mini-Mental State Examination (SMMSE; see Appendix 2). Only if the participant meets the criterion of ≥ 25 points on the SMMSE he/she will be allowed to continue with the remainder of the baseline assessment. Participants who score below 25 points will be informed that they are not eligible to enrol due to scoring below this level on the test. The researcher will advise participants to contact their GP to discuss the result. The one-hour outcome assessment will take place within one week of completing the programme.

Participant characteristics

The following participant characteristics will be collected during the baseline assessment: age (years), gender (male/female), time post-stroke (months), side of lesion (left/right), type of lesion (ischemic/hemorrhagic), self-rated health status (poor, fair, good, very good, excellent), the number of different prescribed medications, if the participant has discussed falls with their health provider (yes/no), if the participant is undertaking/has undertaken any healthy ageing or falls prevention activities (yes/no), recent falls history (fall in the past 12 months, yes/no; injured as a result of a fall, yes/no), and if the participant is able to stand up from the floor without assistance (yes/no).

Outcome measures

The following outcome measures will be administered both at the baseline and outcome assessment:

Questionnaires:

- 1) a bespoke semi-structured survey about the participants' falls prevention knowledge (11 true/false/unsure knowledge statements about falls and falls prevention).

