- 2) the Short Falls-Efficacy Scale-International (FES-I). The FES-I is a validated and reliable 7-item tool which measures confidence in performing a range of activities of daily living without falling.
- 3) The European Quality of Life 5 Dimensions Health Questionnaire (EQ-5D-5L)(32) measures health based on a descriptive system that defines health in terms of five dimensions: mobility, self-care, usual activities, pain/discomfort, and anxiety/depression.
- 4) the Stroke Impact Scale (SIS) assesses stroke-specific quality of life. The SIS is reliable, valid and sensitive to change.(33)

Balance and Mobility tests:

- 5) the Functional Ambulation Classification (FAC) classifies functional ambulation in patients undergoing physical therapy.(34),(35)
- 6) The Berg Balance Test (36) is a psychometrically sound measure of balance impairment for use in poststroke assessment. Given the floor and ceiling effects it is recommended that it is used in conjunction with other balance measures.
- 7) the 4-Square Step Test (37) is a reliable and valid clinical test of dynamic standing balance with high sensitivity and specificity.
- 8) the 5-Times Sit-to-Stand Test (38) is a functional mobility test that has excellent reliability as a measurement tool that correlates with knee flexors muscle strength.(39) (40)

All assessments will be conducted by an experienced physiotherapist.

During the intervention period the participants will be monitored for their adherence to the group exercise programme (attendance register kept by the therapists). The participants will also be asked to keep a record of the time they spend on their home exercise programme, and their fall events (with subsequent injuries) during the intervention period (self-reported through diary, see Appendix 3).

Quantitative data collection

During the outcome assessment participants will be individually interviewed about their experiences with the programme by an experienced physiotherapist who was not involved in delivering the FallMAP sessions. Family members involved with the patient will also be invited to consent (see Appendix 4) an interview. The Patient Information Statement for the family members can be found in Appendix 5.

Depending on the group a one-hour focus group may be undertaken. The topics guide for the interviews can be found in Appendix 6.

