Semi-structured individual interviews of up to an hour's duration each will be held with the two staff members (instructors of the FallMAP sessions) within 2 weeks after all intervention

sessions have been completed. The topics guide for these interviews can be found in Appendix 7.

Study Data and Data Collection Procedures

The data collected during this study will consist of six paper questionnaires, physical (balance and lower limb strength) tests, audio-recordings (in-depth interviews), field notes (observations during the exercise classes), an attendance register and self-report diaries (home-exercise compliance and falls events). All assessments will take place in the exercise venue.

Baseline assessment

First the participants will be asked to provide written informed consent. Then the assessor (a research physiotherapist) will check the participant's level of cognition (duration: 10 minutes). If sufficient for participation (SMMSE ≥ 25 points) the participant characteristics will be collected (duration 10 minutes) followed by the six questionnaires (duration 20 minutes). Finally, the three physical tests will be administered (duration 20 minutes). All questionnaires and physical tests can be found in Appendix 2.

Outcome assessment

After the final (12th) FallMAP session each participant will be invited to undergo a one-hour outcome assessment. The research physiotherapist will repeat the five questionnaires (duration 20 minutes) and the three physical tests (20 minutes). Finally, the in-depth interview will take place (duration: 20-30 minutes).

Staff interviews will take place within two weeks of the final FallMAP session.

Screening, Recruitment and Consent Procedures

Identification and screening of participants

Participants will be identified and recruited through promotion of the project to out-patients from the researchers' local network and (if needed) promotion through the *Council on the Ageing* (COTA WA; <http://www.cotawa.org.au/>) and *Injury Matters* (<https://injurymatters.org.au/>) newsletters.

Recruitment procedures

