In the longer term, participating in this study may have positive impacts on the participants' gait and balance, both physically but also psychologically, in terms of increasing confidence and lessening fear of falling which may have resulted in the adoption of falls risk behaviour, such as abnormal gait and postural balance and slower walking speeds. This study will add to an emerging body of work that is using fear of falling as assessed by a widely validated cross cultural tool (the Falls Efficacy Scale-International) to address the gap in knowledge of how to manage fear of falling successfully in patients after stroke. Participating in this study may further raise awareness amongst the participants of their risk of falling, and may motivate them to continue performing healthy ageing activities that are also good for falls prevention after the study. A potential third benefit for participants of this study is that it will enable them to draw on the existing knowledge about how older adults have low levels of self-perceived risk of falls and generally lack the willingness to take up existing falls prevention strategies.

Withdrawal of participants

Participants have the right to withdraw from the study at any time for any reason, and without giving a reason. Should a participant decide to withdraw from the study, he/she will be asked if they would be happy for the reason for the decision to withdraw to be recorded. The investigator also reserves the right to withdraw participants from the study in the event of inter-current illness, adverse events (AE), serious adverse events (SAE), or if it is judged that it is in the participant's best interests.

9. Adverse Events Reporting

For the purpose of this study, an adverse event (AE) is defined as any untoward medical occurrence in a participant to whom the study procedure or intervention has been administered, including occurrences which are not necessarily caused by or related to that intervention. An AE, therefore, does not necessarily have a causal relationship with the intervention. Medical conditions/diseases present before starting the intervention are only considered adverse events if they worsen after having started participating in the intervention. An AE that is not listed in the study protocol as an expected occurrence in the circumstances of this study is being considered an unexpected AE.

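### No interview is planned for people recorded as withdrawn from the study, so the participant themes for Objective 1 may over-represent those who stayed

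*Combined protocol and SAP*

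**What the plan says.** Section 6 (the subsection on interviews, headed Quantitative data collection like the earlier one) fixes when participants give their views: "During the outcome assessment participants will be individually interviewed about their experiences with the programme". Under Outcome assessment the interview comes last in that visit: "Finally, the in-depth interview will take place (duration: 20-30 minutes".

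The visit is timed in two places. The earlier Quantitative data collection subsection says "The one-hour outcome assessment will take place within one week of completing the programme". Outcome assessment says "After the final (12th) FallMAP session each participant will be invited to undergo a one-hour outcome assessment". On location, Section 6 states "All assessments will take place in the exercise venue".

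Section 8, Withdrawal of participants, gives the only account of leaving: "Participants have the right to withdraw from the study at any time for any reason, and without giving a reason". Someone who chooses to go is asked whether the reason may be recorded. The investigator may also withdraw a person for illness, an adverse or serious adverse event, or because it is in that person's interest. No later contact is described in either case.

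Other material bearing on Objective 1 includes staff and family interviews, "field notes (observations during the exercise classes" and possibly a focus group: "Depending on the group a one-hour focus group may be undertaken".

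**The concern.** Objective 1 in Section 5 is about participants' own experience of the programme: its acceptability (including satisfaction and safety), its practicality, and what hindered or helped. Someone who gave up because the programme did not suit them, or who was withdrawn after an adverse event, is among the best-placed people to describe a barrier or a safety problem. The plan hears from participants at one visit only, and that visit follows the last session. Anyone recorded as having left the study before then has no planned place in it.

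The stake is the balance of the qualitative findings. The themes would describe the programme as seen by those who remained, and the report might not show this. The team discussion in Section 7 that informs the definitive trial is held after the interviews and covers acceptability to patients, so a one-sided set of accounts would feed into it.

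**Working it through.** The plan states no figure on this point, so there is none to reproduce. The check is mainly a reading of the passages together.

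**Step 1. Who is offered an interview?**

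| Situation | What the plan provides | Source |
|---|---|---|
| Attends and stays | Invited to the visit and interview | Section 6, Outcome assessment |
| Misses sessions, stays in the study | Also invited; no attendance condition is set | Section 6, Outcome assessment |
| Stops by choice, recorded as withdrawn | Reason recorded, if the person agrees | Section 8, Withdrawal |
| Withdrawn by the investigator | Nothing further stated | Section 8, Withdrawal |

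The last two rows are the gap. This takes a person withdrawn from the study to be no longer among the participants invited, which is the ordinary meaning. Section 8 has no category for someone who stops the sessions but is willing to keep giving data.

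**Step 2. Do other sources supply the missing account?**

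- Adverse events are asked about before each session (Section 9), so the question does not reach someone who no longer attends.
- Field notes are observations made in class.
- Staff interviews give the view of those who delivered the programme. Family interviews are second-hand.
- The focus group is optional, has no stated time, and is not said to include people who left.
- The completeness check in Section 7 concerns the instruments and their choice for a future trial.

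Each may tell something about a leaver. None is planned as that person's own account.

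**Step 3. Size.** The inputs are n = 10 (Section 6) and progression criterion 1 (Section 7: at least 70% complete 9 of 12 sessions).

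- Each leaver removes 1/10 = 10% of the first-hand accounts.
- Criterion 1 requires 0.70 × 10 = 7 people, so 10 − 7 = 3 may fall short. This does not cap the missing interviews. Sessions run one in one week and two in the next (Section 6, Intervention), so the cumulative count over weeks 1 to 8 is 1, 3, 4, 6, 7, 9, 10, 12. A person attending every session completes the ninth in week 6, with 12 − 9 = 3 sessions left. They can then leave, count as a success and not be interviewed. Conversely, people who fall short may stay and be interviewed.

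**Step 4. How likely is at least one leaver?** The documents give no rate, so this is illustration only. Assuming each person leaves independently with probability p, the chance is 1 − (1 − p)^10:

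| Assumed p | Chance of at least one leaver |
|---|---|
| 0.05 | 1 − 0.95^10 = 40% |
| 0.10 | 1 − 0.90^10 = 65% |
| 0.20 | 1 − 0.80^10 = 89% |
| 0.30 | 1 − 0.70^10 = 97% |

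These figures say how often the gap might come into play. They do not measure bias.

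**The case against.** The strongest reply is that the main case is already covered. The Outcome assessment text invites every participant after the last session without an attendance condition, and the other timing sentence can be read as fixing a date only. This stands. A reader might infer that anyone with poor attendance goes unheard, or that the two timing statements conflict; the documents support neither.

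A second reply is that a person who truly leaves the study has the right to go without explanation, and data collection should then end. This also stands. No plan should seek accounts from people who withdraw consent for data collection. What remains is those withdrawn by the investigator, and those who only wanted to stop exercising but are recorded as withdrawn because no other category exists.

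A third reply is that progression is not blind to leavers: poor attendance enters criterion 1 and intervention-related serious adverse events enter criterion 2. That is right, and neither criterion uses the interviews. But a count of sessions or events does not explain why the programme failed someone, and that is what Objective 1 asks.

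Finally, the appendices (including the topic guides, information statements and consent forms) were not available, and a provision there cannot be excluded. With 10 people and a descriptive analysis, the matter may also prove empty if nobody leaves.

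**Conclusion.** The point holds in limited form. On the text available, people withdrawn by the investigator, or recorded as withdrawn after stopping the sessions, have no planned interview. The Objective 1 participant themes may therefore over-represent those who stayed. The same people have no planned outcome assessment.

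The size is unknown. Each leaver costs 1 of 10 first-hand accounts, and no leavers means no effect. Three stronger conclusions are tempting but unsupported:

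- That criterion 1 limits the loss to 3 of 10. It does not, as shown above.
- That the pre-post summaries are inflated by some amount. Neither the direction nor the size of any effect can be derived from the documents.
- That the progression decision rests on a biased set of interviews. Section 7 places the team discussion after the interviews but does not make them its only basis.

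The conclusion assumes that the unseen appendices add no exit interview and that a withdrawn person is not invited to the final visit. Confidence is medium. The change is worth making because it is cheap and has to be settled in the consent wording before anyone leaves.

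**What to change.** - In Section 8, Withdrawal of participants, distinguish stopping the sessions (by choice or by the investigator's decision) from withdrawing consent for data collection. Keep the right to do either without giving a reason.
- In Section 6, state that the interview and outcome questionnaires are offered at the group's planned end date to everyone who started and has not withdrawn consent for data collection, whatever their attendance. Include the right to decline and a telephone interview as an option, as an exception to the venue rule if that rule is meant to cover interviews. Whether the physical tests are also offered is for the investigators to decide and state.
- Match the consent form to this wording.
- Report the numbers interviewed and assessed out of all who started, without identifying individuals.

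The cost is a short edit to two sections and a line in the consent form. The planned interview time is 10 × 20 to 30 minutes = 200 to 300 minutes, and offering the interview to every starter stays within it. Some who stop will decline, early leavers may recall less by the end date, and people who withdraw consent for data collection will still be missing. The gap narrows but does not close.

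### At baseline the questionnaires follow personal falls and self-rated health questions that are not asked at the outcome visit; reordering the baseline form removes this difference at no cost

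*Combined protocol and SAP*

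**What the plan says.** Section 6 sets the order of both visits. At baseline the SMMSE comes first, then "the participant characteristics will be collected (duration 10 minutes) followed by the six questionnaires (duration 20 minutes", and then the physical tests. Under Participant characteristics the block is tied to one visit: "The following participant characteristics will be collected during the baseline assessment". Its contents include "recent falls history (fall in the past 12 months, yes/no; injured as a result of a fall, yes/no". It also asks about talking to a health provider about falls, taking part in healthy ageing or falls prevention activities, getting up from the floor unaided, and self-rated health.

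Under Outcome assessment the sequence starts with the questionnaires: "The research physiotherapist will repeat the five questionnaires (duration 20 minutes) and the three physical tests (20 minutes". The interview closes the visit: "Finally, the in-depth interview will take place (duration: 20-30 minutes". No characteristics block and no SMMSE are listed there.

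The Outcome measures list opens with "The following outcome measures will be administered both at the baseline and outcome assessment". Its first entry is "a bespoke semi-structured survey about the participants' falls prevention knowledge (11 true/false/unsure knowledge statements about falls and falls prevention" and its second is "the Short Falls-Efficacy Scale-International (FES-I", followed by the EQ-5D-5L and the SIS. The text does not say whether the listed order is the order of administration.

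**The concern.** Self-reported scales can be sensitive to the questions asked just before them. Here the fear-of-falling and quality-of-life scales follow a set of personal falls and health questions at one visit and not at the other. Objective 2 (Section 5) asks whether taking part can improve these outcomes, and the study answers it by comparing the two visits in a single group of 10. A control arm assessed in the same way would share the difference in question order and cancel it. There is no such arm, and the descriptive analysis in Section 7 cannot separate a context effect from a change in the participants. What is at stake is a clean reading of an exploratory before-after change, not a decision about the programme.

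**Working it through.** **1. The two visits side by side (Section 6, Baseline assessment and Outcome assessment).**

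| Position | Baseline | Outcome |
|---|---|---|
| 1 | SMMSE, 10 min | Questionnaires, 20 min |
| 2 | Participant characteristics, 10 min | Physical tests, 20 min |
| 3 | Questionnaires, 20 min | Interview, 20 to 30 min |
| 4 | Physical tests, 20 min | none |

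The interview is last at outcome, so it cannot affect the questionnaires. Nothing before the questionnaires at outcome matches the characteristics block.

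**2. The plan's own figure.** Baseline is stated as one hour (Quantitative data collection). The parts sum to 10 + 10 + 20 + 20 = 60 minutes, so the figure is reproduced.

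**3. How a context effect would enter.** Let s be the average shift in a scale caused by the baseline block, and u the average shift at outcome from whatever has made falls salient by then. The observed mean change is the true mean change plus (u − s). If u and s are equal, nothing is left over. If they differ, the difference passes one-for-one into the mean change, and a larger sample would not shrink it. The documents give neither u nor s.

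**4. Scale, by assumption.** The protocol gives no SD, so work in units of the SD of the paired change. The 95% half-width of the mean change is t(0.975, n − 1)/√n.

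- n = 10: 2.262/3.162 = 0.72
- n = 7, if three participants had no paired data: 2.447/2.646 = 0.92

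| Assumed net shift (SD of change) | Share of half-width, n = 10 | Share of half-width, n = 7 |
|---|---|---|
| 0.1 | 14% | 11% |
| 0.2 | 28% | 22% |
| 0.3 | 42% | 32% |
| 0.5 | 70% | 54% |

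The shifts are assumptions and carry no sign.

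**5. Time after reordering.** Moving the whole block gives 10 + 20 + 10 + 20 = 60 minutes. Splitting it into a minutes before and (10 − a) minutes after the questionnaires gives 10 + a + 20 + (10 − a) + 20 = 60 minutes.

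**6. What cannot be confirmed.** Section 6 speaks of six questionnaires at baseline and five at outcome but lists four. It also speaks of three physical tests but lists four balance and mobility measures. The exact set of instruments ahead of the Short FES-I at each visit is therefore not certain. Appendix 2, which holds the instruments, was not in the text reviewed and may fix their order. The position of the block before the questionnaire set is already fixed in the main text.

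**The case against.** A reader might infer that recalling one's own falls raises reported concern at baseline only, so that the change is biased towards apparent benefit. The documents do not support a direction. They report no order effect for any of these scales. The falls items are yes/no, and a negative answer could reassure. If the cited 45-73% fall incidence applied to this sample over 12 months (an assumption), then 10 × (1 − 0.73) = 2.7 to 10 × (1 − 0.45) = 5.5 of the 10 would report no fall.

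The outcome visit is also not free of falls prompts. Participants will have kept a diary of falls and injuries (Section 6), been asked about adverse events before every session, with falls among the expected ones (Section 9), and had falls education at each session. Their own falls may be as salient at outcome as at baseline, or more so. In the listed order the falls-knowledge survey also comes just before the Short FES-I at both visits, which makes part of the context the same. These arguments stand. They leave the sign and size of (u − s) open, but they do not make the two visits alike.

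A reader might also put the bias at up to about two standard errors. That takes a shift of 0.3 baseline SD and a pre-post correlation of 0.9: √(2 × 0.1/10) = 0.141, and 0.3/0.141 = 2.1. It pairs the two most extreme of several assumed values. With 0.2 SD and a correlation of 0.7 the result is 0.2/0.245 = 0.8. Neither input is in the documents, so the larger figure should not be quoted as a finding.

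Finally, no decision rests on this change. The analysis is mainly descriptive, the progression criteria in Section 7 are attendance and related serious adverse events, and effectiveness is left to a later randomised trial. A one-group change in 10 people cannot be attributed to the programme whatever the question order. This is right, and it is why the point is minor. It is not a reason to keep a difference that costs nothing to remove.

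**Conclusion.** The point holds as a minor, avoidable difference in measurement conditions. The main text establishes that personal falls questions and self-rated health come before the Short FES-I, EQ-5D-5L and SIS at baseline, and that nothing equivalent comes before them at outcome. It does not establish that the scales are affected, in which direction, or by how much. The effect is probably small. Under the assumed range it would lie within the sampling uncertainty of a 10-person mean change, though the upper end of that range would not be negligible. The feasibility conclusions are untouched. The change is worth making because it is free and because this study is meant to inform the assessments of a definitive trial.

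**What to change.** In Section 6, Baseline assessment, and on the baseline case report form:

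- Keep the SMMSE first, followed by the items needed to confirm eligibility (age and time post-stroke).
- Give the questionnaires next.
- Then collect the fall-related items (falls in the past year, injury from a fall, having discussed falls, falls prevention activities, getting up from the floor) and self-rated health, before the physical tests. Self-rated health has to move too; otherwise it still precedes the EQ-5D-5L and SIS at baseline only.
- State the order of the questionnaires and use it at both visits. Reconcile the counts of questionnaires and physical tests at the same time.

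The remaining items (gender, side and type of lesion, number of medications) can stay with the eligibility items. The visits will still differ in that the SMMSE is given at baseline only. This is unavoidable, since it decides whether the assessment continues.

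Cost: one reordered form and a few lines of protocol text. There are no added items, staff, participants or minutes. Baseline stays at 60 minutes, and the falls items are still known before the physical tests begin.
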